8.2.2 Laboratory Evaluations

Individual clinical safety lab (hematology, serum chemistry and serology) values will be listed by visit and summarized using descriptive statistics as appropriate (i.e., mean, median, range, and standard deviation for continuous data and frequency for categorical data). Individual change from baseline (Screening) in laboratory values will be calculated and summarized descriptively. Shift tables from baseline (Screening) to post-dose (Visit 8) will also be produced for the laboratory assessments based on the categories of Low, Normal, and High. A clinically significant change from baseline will be recorded as an AE if deemed appropriate by the Investigator.

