7.5 Recording Adverse Events

All adverse events experienced during the trial, regardless of relationship to study medication, must be recorded on the Adverse Event CRF from the time of patient consent until completion of patients End of Study visit (Visit 9). All serious adverse events will be collected through Visit 9. The Investigator must continue to follow all non-serious events possibly related to the study medication and all serious adverse events until they resolve or until the Investigator assesses them in writing as chronic or stable.

Regardless of relationship to study medication, the event must be recorded on the Adverse Event CRF. Adverse event documentation should include the following information:

- Standard medical terminology for the AE
- Description of adverse event
- Date and time of onset
- Date and time of resolution of the adverse event
- Whether or not the event is ongoing
- Severity of the event
- Relationship between the adverse event and the investigational product
- Description of any actions taken (e.g., medications, treatments)
- Outcome of the AE
- Whether or not the effect was serious and/or unanticipated

Whenever possible, a diagnosis should be given when signs and symptoms are due to common etiology (e.g., cough, runny nose, sneezing, sore throat, and head congestion should be reported as "upper respiratory infection"). For the purposes of this study, hypoglycemic events will be considered adverse events and should be recorded in source and CRF records.

When a diagnosis is not available, each adverse event should be reported separately. For example, "nausea and vomiting" should be split into two separate events.

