8.2 Safety Evaluation

8.2.1 Adverse Events

AEs will be coded using the most current version of MedDRA. The severity of AEs will be graded according to NCI CTCAE version 4.03. AEs will be regarded as “pretreatment” if they occur during the Placebo run-in period. TEAEs are defined as any AE that starts or increases in severity after the first dose of IMP at Visit 3.

The incidence of TEAEs will be tabulated by MedDRA preferred term, system organ class, treatment group, severity, and assigned relationship to IMP. The incidence for each TEAE will be provided as the total number of subjects that experienced the TEAE, as well as the percentage of the population that this represents. If a TEAE is reported more than once for a given subject, the greatest severity and the worst-case attribution will be presented in the summary tables.

TEAEs will be listed for individual subjects, along with information regarding onset and end dates, onset time where available, severity, seriousness, relationship to IMP, action taken, and outcome. A similar listing will be prepared for the pretreatment AEs.

Pretreatment AEs and TEAEs that lead to withdrawal from the study will be separately listed and summarized. Similarly, separate tabulations and listings will be prepared for pretreatment and treatment-emergent SAEs.

Descriptive statistics will be generated as appropriate (i.e., frequency for categorical data). Inferential statistical analysis comparing the AE data between Active treatment and Placebo is not planned.

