8.2.3 Vital Signs

Individual vital sign measurements (seated SBP/DBP, heart rate and oral temperature) will be listed by measurement time and summarized using descriptive statistics as appropriate (i.e., mean, median, range, and standard deviation). Individual change from baseline (screening) in vital sign measurements will be calculated and summarized descriptively. A clinically significant change from baseline will be recorded as a TEAE if deemed appropriate by the Investigator.

8.2.4 12-lead ECG

Individual 12-lead ECG assessments will be listed by visit and summarized using descriptive statistics as appropriate (i.e., mean, median, range, and standard deviation for continuous data and frequency for categorical data).

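### Laboratory change, laboratory shift tables and vital-sign change are measured from Screening, although Visit 3 is labelled baseline and already supplies pre-dose values

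*Combined protocol and SAP*

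**What the plan says.** Section 8.2.2 fixes the laboratory reference: "Individual change from baseline (Screening) in laboratory values will be calculated and summarized descriptively". It then adds: "Shift tables from baseline (Screening) to post-dose (Visit 8) will also be produced for the laboratory assessments". Section 8.2.3 does the same for blood pressure, heart rate and temperature: "Individual change from baseline (screening) in vital sign measurements will be calculated and summarized descriptively".

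Other parts of the document take Visit 3 (week 0) as the starting point. Sections 3.4, 3.4.1 and 3.4.2 attach the word baseline to Visit 3. Section 8.2.1 says: "TEAEs are defined as any AE that starts or increases in severity after the first dose of IMP at Visit 3". It calls adverse events pretreatment "if they occur during the Placebo run-in period". The Synopsis promises changes from baseline at each time point without saying which visit is meant.

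The recording sentence in section 8.2.3 reads: "A clinically significant change from baseline will be recorded as a TEAE if deemed appropriate by the Investigator". The parallel sentences for laboratory values (8.2.2) and physical examination (8.2.5) speak of an AE, not a TEAE. Section 8.2.5 computes no change score, so it is not affected by the table problem.

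**The concern.** Screening and the first active dose are separated by up to six weeks, and the last two of those are a placebo run-in. Whatever moves a laboratory value or blood pressure in that interval cannot be an effect of ORMD-0801. Measured from Screening, it is nevertheless included in every on-treatment change and in the starting category of every shift table.

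There is no control arm against which background change could be set. The reader of a safety table therefore has to take within-subject change more or less at face value, and the reference point matters more than it would in a randomised comparison. At stake is whether the laboratory and vital-sign change tables of a study with safety as its primary endpoint describe what happened on drug.

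**Working it through.** **Inputs**

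- Table 1, nominal days: Screening up to day −42, Visit 2 day −14, Visit 3 day 0, Visit 8 day 84.
- Treatment lasts 12 weeks from Visit 3 (3.4), and the end-of-study visit is 4 weeks later (3.5).
- Inclusion criterion 9 in the Synopsis gives 22 weeks from screening to the last study visit.
- Safety laboratory samples: Screening and Visits 3, 6, 7, 8 and 9 (6.5.5). Blood is drawn before the in-clinic dose (5.2.1). Vital signs precede any blood draw at the same time point (6.5.2).

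**1. Is the run-in inside the 42 days?** Counting 42 days back from Visit 3: 6 + 12 + 4 = 22 weeks, which reproduces the stated span. Counting them back from Visit 2: 6 + 2 + 12 + 4 = 24 weeks, which does not. So the 42 days end at Visit 3 and contain the run-in.

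**2. Off-drug share of the interval to Visit 8**

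- Earliest Screening: 42 / (42 + 84) = 42 / 126 = 33.3%.
- Latest Screening (day −14): 14 / (14 + 84) = 14 / 98 = 14.3%.

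The ±4-day window at Visit 3 widens the 14 to 42 days to about 10 to 46. With Visit 3 as reference, the nominal interval is 84 days and none of it precedes active drug.

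**3. Is the Visit 3 value pre-dose?** Yes. Vital signs come before the blood draw, and the blood draw comes before the capsules.

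**4. Effect on the change tables.** For each subject

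(Visit 8 − Screening) = (Visit 8 − Visit 3) + (Visit 3 − Screening).

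The last term is off-drug and enters every treatment-phase row after the first dose: vital signs at Visits 4 to 8 (5 of 5 rows) and laboratory tests at Visits 6 to 8 (3 of 3 rows).

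**5. Effect on the shift tables**

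| Screening | Visit 3 | Visit 8 | Planned table shows | On drug |
|---|---|---|---|---|
| Normal | High | High | shift | no shift |
| High | Normal | High | no shift | shift |

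**6. What can be recovered.** The Visit 3 row is the off-drug change. For subjects with both values, mean on-drug change = Visit 8 row mean − Visit 3 row mean. The spread cannot be obtained this way. Var(Visit 8 − Visit 3) = Var(Visit 8 − Screening) + Var(Visit 3 − Screening) − 2 × their covariance, and the covariance is not tabulated. The median, range and on-drug shifts do not follow from the rows either. They can be recomputed from the by-visit listings.

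**7. The TEAE sentence.** A vital-sign change from Screening first seen at Visit 2, or before dosing at Visit 3, would be recorded as a TEAE under 8.2.3 but cannot be one under 8.2.1. A change that first arises after the Visit 3 dose satisfies both sections.

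**The case against.** Several points on the other side are sound.

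- **Screening is an explicit choice.** This stands: baseline is defined, and the problem is the choice and its conflict with 3.4 and 8.2.1. A rationale can be imagined. Sections 7.9 and 11.4 count placebo as IMP, and no chemistry or hematology panel is drawn at Visit 2, so Screening is the last full panel before any study capsule. The document does not give this reason. It also does not fit vital signs, which are measured again at Visit 2 before the placebo capsule.
- **The core safety tables are sound.** A reader might infer that the primary safety analysis as a whole starts from the wrong point. It does not. Incidence of TEAEs by term, severity and relationship, and the treatment-emergent SAE and withdrawal tables, are tied to the Visit 3 dose, and pretreatment events have their own listing: "A similar listing will be prepared for the pretreatment AEs". Change from baseline is one display among several.
- **The TEAE wording is a slip.** A reader might infer that pre-drug events will be counted as treatment-emergent. The onset rule in 8.2.1 would largely prevent that, and recording depends on the investigator's judgement. What remains is one sentence that contradicts a definition.
- **The study is exploratory and descriptive, and section 8 defers details to a statistical analysis plan.** This lowers the severity. A deferral does not cancel a reference visit already named, so the text has to be changed rather than supplemented. It does mean one cannot say that no table of on-drug change will ever be produced, only that the current text describes none.

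**Conclusion.** The point holds and should be fixed, with limited harm. As written, the laboratory change, laboratory shift and vital-sign change tables combine 14 to 42 nominal off-drug days with 84 days on drug. They can show a pre-drug shift as a post-dose one and miss a shift that arose on drug.

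The 14.3% to 33.3% is a share of calendar time. A reader might take it as the share of the tabulated change that is spurious, or might suppose that the tables lean towards overstating or understating harm. The documents give no variability, correlation or expected drift between Screening and Visit 3, so neither the size nor the direction can be stated.

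The conclusion rests on the nominal schedule and on the stated order of vital signs, blood draw and dose at Visit 3. It does not extend to tests without a Visit 3 sample, such as HbA1c, which is listed at Screening (3.2), Visit 8 (3.4.4) and end of study (3.5). Those must keep Screening as reference.

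**What to change.** - **Baseline (8.2.2 and 8.2.3).** For change summaries and shift tables, define baseline as the last non-missing value before the first ORMD-0801 dose at Visit 3. Use Screening only where no Visit 3 value exists (for example HbA1c). State that this fallback belongs to the baseline definition, so that it is not read as the substitution of missing data that 8.2.7 rules out.
- **Shift tables.** Build them from Visit 3 to Visit 8.
- **Off-drug change.** Keep Screening-to-Visit 3 change as a separate, labelled row, so that nothing now planned is lost.
- **AE recording.** In 8.2.3 replace TEAE with AE, classified by onset under 8.2.1. In 8.2.2 and 8.2.3, word the recording sentence so that a clinically significant worsening from any earlier value, Screening or Visit 3, can be recorded. Tying it to Screening alone would still miss the High, Normal, High subject.

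The cost is a few lines of protocol and SAP wording and a little table programming. No additional samples, visits or measurements are required.

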3.5 End-of-Study (EOS) (Week 16)/Early Discontinuations

The EOS Visit (Visit 9) will be conducted 4 weeks following the last scheduled treatment Visit. Patients will complete the following EOS evaluations:

- Concomitant medication
- Complete PE, only if the investigator deems it necessary.
- Weight
- ECG, only if the investigator deems it necessary.
- Vital signs (blood pressure, heart rate, oral temperature) will be measured in the sitting position after at least 5 minutes of rest, only if the investigator deems it necessary.

¹ HOMA = The Homeostasis Model Assessment

- Clinical laboratory evaluations (chemistry, hematology)
- Fasting blood glucose and fasting Insulin
- Blood lipids: Total cholesterol, LDL, HDL, Triglycerides
- Adiponectin
- HbA1C
- Urine pregnancy test
- AEs/SAEs assessment

Patients who are discontinued early from the study will complete the EOS evaluations at the time of early discontinuation.

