4 STUDY SUBJECT SELECTION

4.1 Inclusion Criteria

Each subject must meet all of the following criteria to be eligible for the study:

Inclusion Criteria

1. Male or female aged 18-70 years.
2. BMI ≥ 25
3. Known type 2 DM according to American Diabetic Association (one of the three needed): Fasting Plasma Glucose ≥ 126 mg/dl or 2h postprandial (PG) following 75g OGTT ≥ 200 mg/dl or HbA1C $> 6.5-11\%$ ²⁸ or on treatment with at least one and no more than-three of the following oral anti-diabetic medications metformin, sulfonylurea, DPP-4 inhibitors, oral GLP-1 receptor agonists (semaglutide), SGLT-2 inhibitor or Thiazolidinediones (TZDs).
4. Diagnosis of NAFLD by non-invasive determination of hepatic steatosis grade S1, defined as hepatic steatosis $> 8\%$, by MRI- PDFF and CAP FibroScan ≥ 238 dB/m.
5. Liver enzyme abnormalities: ULN ≤ 5 times.
6. Fibrosis score $1 \leq F \leq 3$ as defined by FibroScan measurement (Liver stiffness measurement, LSM) of $6 \leq LSM \leq 12$ kPa.
7. Signature of the written informed consent.
8. Negative pregnancy test at study entry for females of childbearing potential.
9. Females must have a negative urine pregnancy test result at screening, prior to the start of the run-in period, at initiation of active dosing and every 4 weeks following till the end of the study. A negative urine and serum pregnancy test must be obtained prior to active dosing. Males and females of childbearing potential must use two methods of contraception, one of which must be a highly effective method from the time of screening to the last dosing study visit (22 weeks).

Highly effective methods include:

- o combined (estrogen and progestogen containing) hormonal contraception (oral, intravaginal or transdermal) associated with inhibition of ovulation
- o progestogen-only hormonal contraception (oral, injectable or implantable) associated with inhibition of ovulation
- o intrauterine device (IUD)
- o intrauterine hormone-releasing system (IUS)
- o bilateral tubal occlusion

Acceptable methods include:

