4.2 Exclusion Criteria

Subjects who meet any of the following criteria must be excluded from the study:

1. Patients with active (acute or chronic) liver disease other than NASH (e.g. viral hepatitis, genetic hemochromatosis, Wilson disease, alpha-1 antitrypsin deficiency, alcohol liver disease, drug induced liver disease) at the time of enrolment.
2. ALT or AST > 5 times ULN.
3. Abnormal synthetic liver function (serum albumin ≤ 3.5 gm%, INR > 1.3).
4. Known alcohol and/or any other drug abuse or dependence in the last five years.
5. Weight > 120 Kg
6. Known history or presence of clinically significant, cardiovascular, gastrointestinal, metabolic (other than diabetes mellitus), neurologic, pulmonary, endocrine, psychiatric, neoplastic disorder or nephrotic syndrome.
7. History or presence of any disease or condition known to interfere with the absorption, distribution, metabolism or excretion of drugs including bile salt metabolites (e.g. inflammatory bowel disease (IBD), previous intestinal (ileal or colonic) operation, chronic pancreatitis, celiac disease or previous vagotomy).
8. Weight loss of more than 5% within 6 months prior to enrolment.
9. History of bariatric surgery.
10. Uncontrolled blood pressure $BP \geq 150/ \geq 95$.
11. Non type 2 DM (type 1, endocrinopathy, genetic syndromes etc).
12. Patients with HIV.
13. Daily alcohol intake > 20 g/day (2 units/day) for women and > 30 g/day (3 units/day) for men.
14. Treatment with anti-diabetic medications other than at least one and no more than-three of the following medications: metformin, sulfonylurea, DPP-4 inhibitors, oral GLP-1 receptor agonists (semaglutide), SGLT-2 inhibitors, or TZDs
15. Fibrates and statins, not provided on a stable dose in the last 6 months.
16. Patients who are treated with valproic acid, Tamoxifen, methotrexate, amiodarone.
17. Chronic treatment with antibiotics (e.g. Rifaximin).
18. Homeopathic and/or Alternative treatments. Any treatment must be stopped before the screening period.
19. Uncontrolled hypothyroidism defined as Thyroid Stimulating Hormone $> 2X$ the upper limit of normal (ULN). Thyroid dysfunction controlled for at least 6 months prior to screening is permitted.
20. Patients with renal dysfunction: eGFR < 40 ml/min.
21. Unexplained serum creatinine phosphokinase (CPK) $> 3X$ the upper limit of normal (ULN). Patients with a reason for CPK elevation may have the measurement repeated prior to enrolment; a CPK retest $> 3X$ ULN leads to exclusion.

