6.5.5 Clinical Laboratory Tests

Blood for clinical safety laboratory assessments will be collected and processed using standard procedures at Screening and on Visits 3, 6, 7, 8 and 9 and on any unscheduled visit if the investigator deems it necessary. A local laboratory will perform all clinical laboratory tests. In the event of abnormal clinical laboratory values, the Investigator will make a judgment whether or not the abnormality is clinically significant.

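### The laboratory shift table in 8.2.2 runs from Screening to Visit 8 in three categories, so it cannot count patients who worsened on treatment from their own pre-dose value; the effect is modest because other displays remain

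*Combined protocol and SAP*

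**What the plan says.** Section 8.2.2 states: "Shift tables from baseline (Screening) to post-dose (Visit 8) will also be produced for the laboratory assessments based on the categories of Low" (the other two categories being Normal and High). The same section takes Screening as baseline for the individual change summaries. No other laboratory shift table is described in the supplied text.

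The places that bear on it are these.

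- **Entry values.** Inclusion criterion 5 (Section 4.1) reads "Liver enzyme abnormalities: ULN ≤ 5 times". Exclusion criterion 2 (Section 4.2) removes only "ALT or AST > 5 times ULN".
- **Sampling.** Section 6.5.5 draws safety laboratory samples "at Screening and on Visits 3, 6, 7, 8 and 9", and at unscheduled visits where the investigator sees a need. Section 5.2.1 has blood taken before the in-clinic dose, so the Visit 3 sample precedes the first active capsule. Section 3.4.1 labels Visit 3 as baseline.
- **After treatment and early leavers.** Section 3.5 says "The EOS Visit (Visit 9) will be conducted 4 weeks following the last scheduled treatment Visit" and "Patients who are discontinued early from the study will complete the EOS evaluations at the time of early discontinuation"; those evaluations include chemistry and hematology. Section 8.2.7 rules out replacing missing values.
- **Adverse events.** Section 8.2.1 says "TEAEs are defined as any AE that starts or increases in severity after the first dose of IMP at Visit 3". For an event reported more than once in a patient, "the greatest severity and the worst-case attribution will be presented in the summary tables".
- **Other laboratory displays.** Section 8.2.2 lists individual values by visit. The Synopsis (Statistical Methods) tabulates values and changes from baseline at each time point, with minimum and maximum among the statistics.

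Section 8 leaves further detail to a statistical analysis plan. The supplied text has no separate SAP section.

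**The concern.** Safety is the primary endpoint, the patients have liver disease, and there is no concurrent control. A reader will look to the shift table for how many patients' liver tests became worse on the drug. As written it answers a narrower question: how many crossed a normal limit between a Screening sample taken up to six weeks before dosing and one sample at week 12.

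Four things fall outside that question: a rise within the High category, a rise at week 4 or 8 that has settled by week 12, the last value of a patient who left early, and the separation of run-in change from on-drug change. The last of these also sets two parts of the plan against each other. A laboratory rise that starts in the placebo run-in and persists is pretreatment in the adverse event tables but a post-dose shift in 8.2.2.

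**Working it through.** The plan gives no figure to reproduce here. The size of up to 40 has no formula behind it, and Section 8.1 says the study is not powered. The checks are counts from the schedule, plus illustrations whose assumptions are marked.

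**1. Visits used.** Visit 3 is pre-dose and Visit 9 is off treatment, so the scheduled on-treatment samples are Visits 6, 7 and 8. With 40 patients, 3 × 40 = 120 patient-visits. The table uses 40 and leaves out 80 (80/120 = 67%).

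If an excursion occurs independently at each visit with probability p (assumed), the share of patients with any excursion who show it at Visit 8 is p / (1 − (1 − p)³). For p = 0.02 this is 0.02/0.0588 = 34%; for p = 0.20 it is 0.20/0.488 = 41%. A rise that persists to week 12 is not missed.

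**2. Time before the first active dose.** Screening lies between day −42 and the start of run-in at day −14, and Visit 8 is at day 84 (visit windows ignored).

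- Latest Screening: 14/(14 + 84) = 14/98 = 14%.
- Earliest Screening: 42/(42 + 84) = 42/126 = 33%.
- With a Visit 3 pre-dose baseline: 0/84 = 0.

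The 42-day reading agrees with the 22-week total in inclusion criterion 9 (6 + 12 + 4 = 22).

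**3. High at entry.** The documents give no distribution. For illustration, assume an ALT-like log-normal value with median 0.8 or 1.2 × ULN, between-patient log SD 0.5, within-patient log SD 0.15 to 0.35, and the 5 × ULN cap at Screening. Then 33% to 64% of patients start High. If the Visit 8 value truly doubles, 33% to 64% of the patients affected appear as High-to-High.

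**4. Run-in change.** Under the same model with no drug effect, 2.4 to 5.1 of 40 patients shift from Normal at Screening to High at Visit 8, and 44% to 54% of them were already High at the pre-dose Visit 3 sample. In this model the visits are interchangeable apart from the entry cap. Moving the baseline would therefore not much change the number of chance shifts; it would make each shift refer to time on active drug.

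**5. Early leavers.** No dropout rate is stated. An assumed 5% to 20% gives 0.05 × 40 = 2 to 0.20 × 40 = 8 patients without a Visit 8 value.

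**6. Cost of a worst-value table.** Assume all 40 start Normal, 2.5% of samples exceed ULN by chance, and samples are independent. Visit 8 alone gives 0.025 × 40 = 1.0 patient per analyte. The worst of three gives (1 − 0.975³) × 40 = 0.0731 × 40 = 2.9. Unscheduled samples would add to this.

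**The case against.** The strongest reply is that nothing is hidden. Changes from baseline are to be tabulated at each time point with minimum and maximum, so a rise from 2 to 12 × ULN at Visit 6 should appear as that visit's maximum change and in the listing, even in a patient High at entry. With at most 40 patients in one arm, listings can be read line by line. Section 7.2 counts abnormal laboratory findings as possible adverse events, and events leading to withdrawal are listed separately. This stands, and it is why the effect is modest. Two gaps remain. A maximum shows the largest change, not how many patients worsened. And Sections 6.5.5 and 8.2.2 leave it to the investigator whether a laboratory change matters enough to be recorded as an event.

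A second reply defends Screening: it is the only scheduled chemistry and hematology sample before any capsule, placebo included, and Sections 8.2.2, 8.2.3 and 8.2.5 all use it as baseline. Visit 3 values are also summarized as their own time point. That is a fair rationale. But Section 8.2.1 starts treatment-emergence at Visit 3, Section 3.4.1 calls Visit 3 baseline, and the change summaries in 8.2.2 carry the same Screening anchor, so they do not cure the problem.

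Third, a SAP could add tables, and 8.2.2 does not exclude others. True; the point is limited to the supplied text. The three categories, the single visit and the Screening baseline are nevertheless stated choices, which a SAP would have to change or supplement. Early leavers are a matter of silence combined with the no-substitution rule in 8.2.7.

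Some stronger readings are tempting but unsupported. A reader might infer that a liver signal would go unseen, that 67% of on-treatment data are unreported, or that 33% of shifts are misclassified. The first two are contradicted by the listings and by-visit tables; the shares of visits and days are not rates of missed or false signals. Nor do the documents establish that every patient starts High: criterion 5 may require an abnormal enzyme or may only cap it.

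**Conclusion.** The point holds for the shift table as written, as an inexpensive improvement and not as a flaw that loses data. The table cannot show further upward worsening in patients already High (nor further falls in those already Low), it uses one of three on-treatment visits, it does not place early-termination samples, and it dates change from Screening. The inconsistency over baseline between 8.2.2, 3.4.1 and 8.2.1 is real and needs reconciling; it also affects the change-from-baseline summaries.

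The counts (80 of 120 patient-visits; 14 to 42 pre-treatment days) follow from the schedule and 40 patients. The proportions High at entry, the chance-shift figures and the dropout range rest on assumptions and only illustrate scale. What is missing from the planned outputs is a count of patients who ever worsened on treatment from their own pre-dose value.

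**What to change.** In Section 8.2.2 or the SAP:

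- Define baseline, for both the change summaries and the shift tables, as the last value before the first active dose: the Visit 3 pre-dose sample, otherwise Screening. Reconcile this with Section 3.4.1; it then agrees with Section 8.2.1.
- Keep the Visit 8 shift table.
- Add a table of baseline against the worst on-treatment value, taken over Visits 6 to 8, unscheduled samples and early-termination samples. Show off-treatment Visit 9 separately and include a column for patients with no post-dose value.
- For ALT, AST, ALP and bilirubin use multiples-of-ULN bands, with cut-points set by the sponsor before database lock.

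The cost is wording and some extra table rows, with no new visits or samples. The drawback is more chance excursions: about 2.9 against 1.0 Normal-to-High patients per analyte under the assumptions in step 6, and more once unscheduled samples are included. With no control arm, the worst-value table should therefore be read beside the Visit 8 table, not in place of it.

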3.7 Self-Monitoring Fasting Blood Glucose and Patient Diaries

All patients will self-monitor fasting morning blood glucose levels three (3) times weekly during the run-in and treatment period. Monitoring must be performed at the same time each designated day (\pm 10 minutes) prior any caloric intake. Patients will be required to record the values in a patient diary and bring the diary to each clinic visit; Information recorded for the fasting blood glucose will be reviewed by the clinical research coordinator for completeness and transcribed onto CRF's. During the study, both fasting finger stick glucose and laboratory fasting plasma glucose will be obtained. Adverse events including hypoglycemia will be monitored from the self-monitoring blood glucose diary and recorded in the CRF.

If a fasting blood glucose measures greater than or equal to 270 mg/dL (15 mmol/L) during daily self-monitoring or during any in-clinic visit, the patient will be required to contact the clinic to report the value. The patient may be required to return for an unscheduled visit to the clinic for a repeat measurement of fasting blood glucose within one week after the original measurement. If the patient is invited for an unscheduled visit, blood will be drawn and sent to lab for plasma glucose determination. If the repeat measurement is also greater than or equal to 270 mg/dL, the patient will be discontinued from treatment with study drug and offered rescue medication. The patient will continue to be seen for all remaining study visits, if possible.

If a fasting blood glucose value is <70 mg/dL, the patient should drink 1 cup of orange juice or swallow 3-4 glucose tablets. The patient must check his blood sugar after 10 min and if the blood glucose level does not raise, the patients needs to drink another cup of orange juice or swallow 3-4 glucose tablets. Blood sugar must be checked again after 10 minutes. The patient must call to report this event to the study site and record all blood glucose levels in the diary.

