7.3 Adverse Events of Special Interest

7.3.1 Adverse Events of Hypoglycemia

The CTCAE (version 5.0) criteria for mild, moderate, and severe hypoglycemia based on blood glucose will be used, as shown below:

Mild: < 70 – 55 mg/dL (< 3.8 - 3.0 mmol/L)

Moderate: < 55 – 40 mg/dL (< 3.0 - 2.2 mmol/L)

Severe: < 40 – 30 mg/dL (< 2.2 - 1.7 mmol/L)

Life Threatening: < 30 mg/dL (< 1.7 mmol/L)

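### Hypoglycemia is value-based in Sections 7.3.1 and 7.5 but discretionary for laboratory glucose in Section 8.2.2, and no planned table counts it by the Section 7.3.1 glucose bands

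*Combined protocol and SAP*

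**What the plan says.** Section 7.3.1, the only entry under adverse events of special interest, says that CTCAE version 5.0 "criteria for mild, moderate, and severe hypoglycemia based on blood glucose will be used, as shown below". The first band is "Mild: < 70 – 55 mg/dL". It asks for no symptoms and does not separate meter from laboratory values. Section 7.5 adds: "For the purposes of this study, hypoglycemic events will be considered adverse events and should be recorded in source and CRF records".

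Glucose is also in the serum chemistry panel of Section 6.5.5.1. For abnormal results from that panel, Section 6.5.5 says "the Investigator will make a judgment whether or not the abnormality is clinically significant". Section 8.2.2 then says: "A clinically significant change from baseline will be recorded as an AE if deemed appropriate by the Investigator". Neither section exempts glucose or refers to Section 7.3.1 or 7.5.

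Section 3.7 governs the diary. Patients measure fasting glucose three times a week. A fasting value below 70 mg/dL must be reported to the site, and hypoglycemia is monitored from the diary and recorded in the CRF. Symptom-triggered readings also go into the diary. The transcription rule, however, names the fasting values: "Information recorded for the fasting blood glucose will be reviewed by the clinical research coordinator for completeness and transcribed onto" the CRF.

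On analysis, Section 8.2.1 says: "The incidence of TEAEs will be tabulated by MedDRA preferred term, system organ class, treatment group, severity, and assigned relationship to IMP". It grades severity by CTCAE version 4.03 and does not mention the Section 7.3.1 bands.

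**The concern.** Take a symptom-free laboratory glucose of 62 mg/dL at Visit 7. Under Sections 7.3.1 and 7.5 read together, it is a mild hypoglycemic event. Under Section 8.2.2, it becomes an adverse event if the investigator finds the change clinically significant and appropriate to record. Nothing says which text prevails, and 7 or 8 sites in three countries may answer differently.

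The database does not settle the matter afterwards. A symptom-triggered fingerstick, which may follow the dose, has no stated route into the CRF except through an adverse event entry. The items that Sections 7.5 and 7.5.1 require for such an entry do not include a glucose value. The incidence in Section 8.2.1 is built from adverse event entries, so the reported figure for the main expected risk of an insulin product rests partly on entry practice where a measured value could be used. With one arm and up to 40 patients, each patient is 1/40 = 2.5 percentage points, and no concurrent control would show an undercount.

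**Working it through.** The plan gives no expected hypoglycemia rate or event count, so there is no figure to reproduce. The check is how many readings fall under the discretionary rule, and how many patients could turn on it.

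**Inputs**
- Patients: up to 40 (Section 8.1).
- Diary: 3 readings a week (Section 3.7) over 12 treatment weeks (Section 3.4), so 3 × 12 = 36 per patient.
- Laboratory: Visits 3, 6, 7, 8 and 9 after screening (Section 6.5.5). Blood is drawn before dosing (Section 5.2.1), so Visit 3 precedes the first active dose. That leaves 3 on treatment, or 4 with Visit 9.
- Chance p that a reading is below 70 mg/dL: not in the documents; assumed 1% to 3%.

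**Share of readings under Section 8.2.2**
- On treatment: 3/(36 + 3) = 3/39 = 7.7%.
- With Visit 9: 4/(36 + 4) = 4/40 = 10.0%.
- For 40 patients: 40 × 36 = 1,440 diary readings, and 40 × 3 = 120 laboratory readings (40 × 4 = 160 with Visit 9).

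**Patients whose only low is a laboratory value**

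With independent readings, a patient has no diary low but at least one laboratory low with probability (1 − p)^36 − (1 − p)^39. If investigators enter none of the laboratory lows, these patients are lost from the count.

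| p | (1 − p)^36 | (1 − p)^39 | Difference | × 40 patients | Points |
|---|---|---|---|---|---|
| 1% | 0.6964 | 0.6757 | 0.0207 | 0.83 | 2.1 |
| 3% | 0.3340 | 0.3049 | 0.0292 | 1.17 | 2.9 |

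For scale, the diary alone would give 40 × (1 − 0.6964) = 12.1 patients with a low at p = 1%, and 40 × (1 − 0.3340) = 26.6 at p = 3%.

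With Visit 9 the exponent 39 becomes 40, and the loss is 1.1 patients at p = 1% and 1.5 at p = 3%. Over p = 0.5%, 1%, 2% and 5% it is 0.7, 1.1, 1.5 and 1.2 patients.

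**What cannot be counted.** Symptom-triggered and unscheduled readings have no scheduled number, so their contribution cannot be calculated from the documents.

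**The case against.** The strongest reply is that Section 7.5 is a rule made for this study, while the Section 8.2.2 sentence is general wording that recurs almost unchanged for vital signs and physical examination. On that reading the specific rule prevails. Section 7 supports it: adverse events found by laboratory test or recorded in the diary are to be collected, and Section 7.2 counts abnormal laboratory findings among possible adverse events. Section 6.5.5 asks only for a judgment of clinical significance and sets no condition for recording an adverse event. This is a fair reading, but no text states it. Section 7.3.1 is a grading scale, and hypoglycemic event is not formally defined.

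Fasting plasma glucose also has its own Section 6.5.6, with no discretion clause. The 120 laboratory values are therefore an upper limit on what Section 8.2.2 governs, although panel glucose from the same visits remains under it.

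The values are not hidden. Section 8.2.2 lists laboratory results by visit, and Section 8.2.7 promises descriptive statistics and listings for all data. That stands, but neither gives an incidence of hypoglycemia. The planned shift table runs only from Screening to Visit 8, in Low, Normal and High categories not tied to 70 mg/dL. Section 8 leaves further detail to the statistical analysis plan, so a suitable table could still be specified; the text available does not contain one.

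A reader might infer that the whole hypoglycemia count depends on site judgment instead of recorded glucose. The documents do not support that: 36 of 39 scheduled on-treatment readings are diary values under Section 3.7, which has no discretion clause, and the laboratory samples are fasting and pre-dose.

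**Conclusion.** The point holds as a modest one. Sections 7.3.1 and 7.5 are not reconciled with Section 8.2.2 for a low laboratory glucose, symptom-triggered diary readings have no stated route to the database other than an adverse event entry, and the event of special interest is never tabulated by its own bands.

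The part that can be sized is about 1 patient of 40, or 2 to 3 percentage points on treatment. This rests on an assumed 1% to 3% of readings below 70 mg/dL, independent readings, complete diaries, and no laboratory low entered as an event. Clustering of lows within patients would tend to shrink it; incomplete diaries would enlarge it.

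A reader might instead take the chance of any laboratory low in three samples, 1 − 0.99^3 = 3.0% to 1 − 0.97^3 = 8.7%, as the undercount. That would require every such patient to have no low in the diary, which nothing in the documents suggests. Nor do they show that a low reported rate would merely reflect reporting habit. They show only that the planned tables could not rule that out for the readings affected.

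**What to change.** 1. Reconcile Section 8.2.2 with Sections 7.3.1 and 7.5, and cross-refer Section 6.5.5, so that one stated rule says when a recorded glucose in a Section 7.3.1 band counts as a hypoglycemic event.
2. Add to Section 8.2.1 a table derived by program: patients with any glucose in each Section 7.3.1 band after the first Visit 3 dose, by source (laboratory, clinic, diary, unscheduled), beside investigator-reported hypoglycemia.
3. In Section 3.7, have all diary glucose readings transcribed to the CRF with date and time, including symptom-triggered ones.

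The cost is protocol wording, one derived dataset and some extra CRF entry. No visit or test is added. The reported incidence may come out slightly higher. The first item alone removes the textual conflict; the second and third make the count less dependent on judgment.
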